## **D. Secondary Efficacy Analyses**

### **1. Key Secondary Efficacy Analysis**

The key secondary analysis will be based on the FAS and will use control-based PMM-MI for both categorical and continuous endpoints to handle missing data. The key secondary analysis endpoints are as following:

- Percent of subjects achieving a vIGA score of 0 or 1 at Week 16. Analyzed as a binary

endpoint.

- Percent of subjects achieving EASI-75, defined as a 75% reduction in EASI from baseline to Week 16. Analyzed as a binary endpoint.
- Percentage change from baseline in PP-NRS from an itch daily e-Diary at Week 16. Analyzed as a continuous endpoint.

### Binary endpoints

The key secondary efficacy binary endpoint will be analyzed with a logistic model. The model will include treatment group, the randomization stratification factors of baseline vIGA scores (3 or 4) and prior dupilumab or tralokinumab use (yes or no), and the baseline score as covariate (if not previously included).

The estimate and standard error of the log odds ratio will be evaluated for each of the imputed datasets and combined in PROC MIANALYZE using Rubin's formula. The combined results will be back transformed such that the odds ratio, 95% CI and p-value are reported.

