9.4.2.1 Secondary Efficacy Analysis

For continuous secondary endpoints, the same model as discussed for the primary analyses will be followed. For binary secondary endpoints, a logistic regression model with treatment group, baseline vIGA scores, randomization stratification factors, study sites as factors and baseline score as a covariate will be used.

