#### C. Sample Size Predictions

- [Redacted]
- [Redacted]
- [Redacted]
- [Redacted]

Based on the assumptions above and using a two-sample t-test, a sample size of 60 subjects per treatment group is needed to detect the treatment effect on the primary endpoint between RPT193 and placebo. Assuming a 10% drop out rate, a total sample size of 268 subjects (67 per treatment group) will be needed.

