### A. Efficacy Assessments

#### 1. Eczema Area Severity Index (EASI)

The EASI is a clinician assessment that is collected at Screening/ Visit 1, Baseline/ Visit 2, Visit 3/ Week 2, Visit 4/ Week 4, Visit 5/ Week 8, Visit 6/ Week 12, Visit 7/ Week 16, Visit 8/ Week 18, Week 9/ Week 20 and Visit 10/ Week 24 using the e-Diary.

The EASI is a composite score ranging from 0 to 72 that takes into account the degree of erythema, induration/infiltration (papules), excoriation, and lichenification (each scored as =None, 1=Mild, 2=Moderate 3=Sever) for each of 4 body regions (head and neck, trunk, upper extremities and lower extremities), with adjustment for the percentage of BSA (assessed by the palmar method) involved for each body region ( 0= 0%, 1=1-9%, 2=10-29%, 3=30-29%, 4= 50-69%, 5=70-89%, 6=90-100%) and for the proportion of the body region to the whole body (.1 for head and neck, .3 for trunk, .2 for upper extremities and .4 for lower extremities)

The domain score will be calculated in the ADaM dataset when all assessments are completed. The following is the calculation for each body region:

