### C. Primary Efficacy Analysis

The primary endpoint is the percent change in EASI from baseline to Week 16. The primary analysis will be based on the FAS and will use control-based PMM-MI to handle missing data.

The primary efficacy endpoint will be analyzed with an ANCOVA model. The model will include treatment group (each RPT193 dose vs. placebo), the randomization stratification factors of baseline vIGA score (3,4), and prior dupilumab or tralokinumab use (yes or no), and baseline EASI score as a covariate.

For each imputed dataset the least square (LS) mean, and LS mean difference in the percent change from baseline between each RPT193 dose level and placebo along with the corresponding estimated standard error will be reported. These results will be combined in PROC MIANALYZE using Rubin's formula and the resulting p-value will be used for inference at the 0.05 level of significance. The LS mean and LS mean difference along with the 95% confidence interval (CI) and p-value will be reported.

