### SAS example code for PMM-MI (NMAR):

#### EASI\_PP-NRS

```
proc mi data =data_in out =data_out seed=1277282 nimpute = 1 min=0 by _imputation_;  
  class trt01p base_VIGA prioruse;  
  var base_EASI week2-16;  
  monotone reg(week16 = base_EASI week2-12 trt01p base_VIGA prioruse);  
  mnar model(week16/ modelobs=(trt01p='placebo'));  
run;
```

VIGA

```
proc mi data =data_in out =data_out seed=1277282 nimpute = 1 min=0 max=4
  by _imputation_;
  class trt01p base_VIGA prioruse;
  var base_VIGA week2-16;
  monotone_logistic(week16 = week2-12 trt01p base_VIGA prioruse);
  mnar model(week16/ modelobs=(trt01p='placebo'));
run;
```

SAS example code for imputed results combinations:

```
proc glm data = data_mi;
  model week16 = base_EASI week2-12 trt01p base_VIGA prioruse;
  by _imputation_;
  ods output ParameterEstimates=mxparms;
run;

proc mi analyze parms=mxparms;
  class trt01p;
  modeleffects Intercept base_EASI week2-12 trt01p base_VIGA prioruse;
run;
```

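### The key secondary vIGA 0/1 model takes baseline severity only as vIGA 3 versus 4; naming baseline EASI as a covariate could recover a little power at small cost

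*SAP*

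**What the plan says.** SAP VI.D.1 (Binary endpoints) specifies a logistic model. Besides a term for randomized arm, its factors are "the randomization stratification factors of baseline vIGA scores (3 or 4) and prior dupilumab or tralokinumab use (yes or no". A short clause then decides whether anything more enters, and it reads "and the baseline score as covariate (if not previously included". Protocol 9.4.2.1 is no more specific: "baseline vIGA scores, randomization stratification factors, study sites as factors and baseline score as a covariate will be used". Neither text says which variable the baseline score is for each endpoint.

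The primary ANCOVA in SAP VI.C names its covariate outright: "and baseline EASI score as a covariate". SAP VI.A.1 shows that the value will be available: "The EASI is a clinician assessment that is collected at Screening/ Visit 1, Baseline/ Visit 2".

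The Appendix II example code for imputing vIGA has no EASI term: "monotone_logistic(week16 = week2-12 trt01p base_VIGA prioruse". The sensitivity analyses for vIGA 0/1 in SAP VI.B and VI.D.1 change the analysis set or the handling of missing data. None adds baseline EASI.

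SAP II.A defines the summary measure for vIGA 0/1 as a difference in percentages; VI.D.1 reports an odds ratio. SAP IV.G leaves secondary endpoints unadjusted for multiplicity.

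**The concern.** The rule that adds the baseline score only when it is not already present works differently for the two binary key secondary endpoints. For EASI-75 it brings in baseline EASI. For vIGA 0/1 it brings in nothing, because baseline vIGA is a stratification factor.

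The vIGA 0/1 model therefore separates subjects by severity only as 3 or 4. Baseline EASI must be at least 16 (Protocol 5.1, criterion 6) on a scale that runs to 72 (SAP VI.A.1), so it can differ widely among subjects with the same vIGA. If it predicts reaching clear or almost clear within a vIGA level, leaving it out of a logistic model pulls the treatment log odds ratio toward zero and costs some power. At stake is a small amount of precision in each dose comparison on a key secondary endpoint, obtainable from a value already in the data set.

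**Working it through.** **Inputs from the documents.** SAP III.C: "a sample size of 60 subjects per treatment group is needed to detect the treatment effect on the primary endpoint", and "Assuming a 10% drop out rate, a total sample size of 268 subjects (67 per treatment group) will be needed". Allocation is 1:1:1:1 (SAP III.D). The two-sided 0.05 level is set for the primary endpoint (Protocol 9.4.2.2, SAP IV.G); here it is taken as the nominal level for vIGA 0/1.

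**Assumptions, not in the documents.** Response rates; the EASI slope; 40% of subjects at vIGA 4; 20% with prior use (the approximate cap in Protocol 6.3); log-odds effects of −0.7 for vIGA 4 and −0.2 for prior use; right-skewed EASI within each vIGA level; no missing data.

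**Step 1, the plan's own figure.** 60 / (1 − 0.10) = 66.7, rounded up to 67; 4 × 67 = 268. This matches the SAP. The 60 cannot be re-derived because its inputs are redacted. No power is stated for vIGA 0/1.

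**Step 2, what the covariate rule yields.**

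| Endpoint | Stratification factors | Added baseline score |
|---|---|---|
| EASI-75 | vIGA 3/4, prior use | baseline EASI |
| vIGA 0/1 | vIGA 3/4, prior use | none (vIGA already in) |

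**Step 3, anchor.** Unadjusted power for two proportions is Φ{[|p₂ − p₁|√n − 1.96√(2p̄(1 − p̄))] / √(p₁(1 − p₁) + p₂(1 − p₂))}. With n = 67, p₁ = 0.10 and p₂ = 0.25, p̄ = 0.175, and this is Φ[(1.228 − 1.053) / 0.527] = Φ(0.33) = 63.0%. The same formula gives 83.3% for 10% vs 30% and 76.8% for 15% vs 35%.

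**Step 4, simulation.** One dose against placebo, 67 per arm, 6000 trials per row. Data come from logit(p) = a + b·treatment + c·vIGA4 + d·prior use + s·e, where e is baseline EASI standardized within vIGA level. Model A omits e and model B includes it; both are fitted to the same data and reject when |b/SE| > 1.96. Each power figure has a Monte Carlo error of about 0.6 point, and the paired differences have less. Differences were taken before rounding.

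| Rates | Slope s | A (%) | B (%) | B − A (points) |
|---|---|---|---|---|
| 10 vs 25 | 0 | 63.1 | 63.2 | 0.1 |
| | −0.25 | 63.4 | 63.8 | 0.4 |
| | −0.5 | 63.6 | 64.6 | 1.1 |
| | −0.75 | 63.2 | 65.9 | 2.7 |
| | −1.0 | 62.7 | 66.9 | 4.2 |
| 10 vs 30 | 0 | 84.5 | 84.5 | 0.0 |
| | −0.25 | 84.6 | 84.7 | 0.1 |
| | −0.5 | 83.5 | 84.4 | 0.9 |
| | −0.75 | 84.6 | 86.4 | 1.7 |
| | −1.0 | 83.7 | 86.5 | 2.8 |
| 15 vs 35 | 0 | 77.5 | 77.3 | −0.2 |
| | −0.25 | 77.0 | 77.6 | 0.5 |
| | −0.5 | 77.6 | 78.8 | 1.2 |
| | −0.75 | 78.2 | 80.0 | 1.8 |
| | −1.0 | 77.3 | 80.7 | 3.4 |

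At slope 0, model A gives 63.1, 84.5 and 77.5, close to the anchors in step 3. The change is −0.2 to +1.2 points for slopes of 0 to −0.5, and +1.7 to +4.2 points for −0.75 to −1.0.

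**Step 5, why the gain is small.** At 10% vs 25% and slope −0.5, the median log odds ratio rises from 1.154 to 1.196 and its standard error from 0.514 to 0.525. The ratio goes from 1.154 / 0.514 = 2.25 to 1.196 / 0.525 = 2.28. Most of the larger estimate is offset by the larger standard error.

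**Step 6, type I error.** With equal rates of 10%, A and B reject 3.4% and 3.6% at slope 0, and 3.9% and 4.0% at −0.5. With equal rates of 20%, they reject 4.5% and 4.8%, then 5.1% and 5.2%.

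**Step 7, four arms.** A separate simulation with all four arms (67 each, 10% vs 28%, no missing data) gave changes of −0.2, +0.7, +1.1 and +2.7 points when the log odds fall by 0, 0.3, 0.6 and 0.9 per SD. The result was the same on the raw or log EASI scale. Type I error was 3% to 4% in both models.

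**The case against.** The case against acting is substantial.

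- **The rule is consistent.** The SAP adjusts each binary endpoint for the stratification factors and that endpoint's own baseline score. The primary model has EASI because EASI is its endpoint. A reader might infer that the vIGA model contradicts the primary model; it does not. This stands.
- **No loss is demonstrated.** A reader might infer that power is definitely being lost. That needs the prognostic strength of EASI within a vIGA level, and no section gives it. At weak to moderate slopes the gain is about 1 point or less. This stands, and it is why the point is conditional.
- **Adjustment is not free.** The four-arm model already carries three treatment terms, vIGA and prior use. At an assumed 10% placebo rate, 67 subjects yield about 7 responders. A reader might also infer that the plan expects few responders; the documents state no vIGA 0/1 rates. The simulated cost at slope 0 is at most 0.2 point, so the cost is small but not nil.
- **The planned analysis is not fully simulated.** It uses control-based multiple imputation with 100 data sets, while the simulations assume complete data. The two-arm limitation is answered by step 7. The missing-data limitation stands, so changing the imputation model has no numerical support beyond keeping it consistent with the analysis model.
- **The odds ratio moves.** Part of its increase is non-collapsibility: the adjusted odds ratio is a different parameter, further from the difference in percentages in SAP II.A. This stands and is addressed in the fix.
- **Little turns on it.** The trial is sized on the primary endpoint, and vIGA 0/1 is tested outside the gatekeeping sequence. This stands.

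**Conclusion.** This is an optional improvement, not an error. On the natural reading of SAP VI.D.1, the vIGA 0/1 model adjusts for severity only through vIGA 3 versus 4, with baseline EASI at hand and unused. The planned model is valid, adjusts for severity on the endpoint's own scale, and shows no inflation of type I error.

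The power that may be given up is about 0 to 1 point if EASI is weakly to moderately prognostic beyond vIGA, and about 2 to 4 points if strongly prognostic. If EASI is not prognostic, including it makes essentially no difference. These sizes rest on assumed slopes and response rates and on complete data. The documents do not support a claim that the analysis is biased, that a loss is certain, or that EASI-75 is affected.

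**What to change.** In SAP VI.D.1, name baseline EASI as a continuous covariate for vIGA 0/1, alongside baseline vIGA and prior dupilumab or tralokinumab use. State the scale; untransformed would match the primary model. Naming the variable also removes any doubt about what the baseline score means for each endpoint. Add baseline EASI to the vIGA imputation code in Appendix II so that the imputation and analysis models use the same covariates.

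Because SAP II.A asks for a difference in percentages, report a standardized risk difference from the adjusted model beside the odds ratio.

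SAP I.B allows changes until unblinding, so this should be final before the Week 16 efficacy analysis in SAP IV.F goes to the unblinded group. The cost is one term in two models, one more parameter to estimate, and an odds ratio that is conditional on baseline EASI.

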### A. Estimand

The main estimands associated with the primary and key secondary endpoints to support regulatory decisions are described in the following table:

Attribute	Description
Treatment	RPT 193-02 (50mg, 200mg, 400mg) and Placebo
Population	Adult subjects with moderate-to-severe AD as defined by the inclusion/exclusion criteria
Endpoint	
Primary Endpoint
 
 
% change in Eczema Area Severity Index (EASI) from baseline at Week 16
 
 
Key Secondary Endpoints
 
 
% of subjects achieving a Validated Investigator Global Assessment (vIGA) score of 0 or 1 at Week 16
 
% of subjects achieving EASI-75, defined as a 75% reduction in EASI from baseline to Week 16
 
% change from baseline in PP-NRS from an itch daily e-Diary at Week 16.
 

Intercurrent Events	
 
Early termination of study treatment: Subjects who discontinue from the study treatment prior to Week 16 will be analyzed by the treatment policy strategy, i.e., all data collected after termination of study treatment but prior to rescue medication will be included in the analysis. Missing post discontinuation values will be imputed according to details provided below.
 
Use of rescue medications: Subjects who use rescue medication during the 16-week treatment period will be analyzed by the hypothetical strategy. All EASI/vIGA/PP-NRS scores collected after the start of rescue medication will be set to missing. The missing data after the use of rescue medication will be imputed to follow a similar profile as the placebo group.
 

Population-level Summary	
Primary Endpoint
 
 
Difference in mean percent change from baseline in EASI score between each RPT193 dose and placebo at Week 16.
 
 
Key Secondary Endpoints
 
 
Difference in percentage of subject achieving vIGA of 0 or 1 between each RPT193 dose and placebo at Week 16.
 
Difference in percentage of subject achieving EASI-75 between each RPT193 dose and placebo at Week 16.
 
Difference in mean percent change from baseline in PP-NRS
 

	between each RPT193 dose and placebo at Week 16.
--	--

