#### **Control-based PMM-MI procedures for EASI, PP-NRS, and vIGA under MNAR**

Similar to MI under MAR, but for EASI, PP-NRS, and vIGA, data collected after the intercurrent events of rescue medication or treatment discontinuation in the RPT193 arm will be assumed missing not at random (MNAR) and resemble missing data from subjects from the placebo arm who do not discontinue treatment permanently/receive rescue medication. Imputation of missing data at Week 16 will be done using a control-based Pattern Mixture Model Multiple Imputation (PMM-IM) where missing data in the study drug (RPT-193) arm as well as the placebo arm will be imputed from observed data in the placebo arm.

The intermittent missing data will be imputed separately for each treatment group using the Markov Chain Monte Carlo (MCMC) method implemented with the SAS PROC MI procedure. 100 imputed datasets will be generated.

For each of the 100 datasets a monotone missing data pattern will be achieved. The monotone missing values will then be imputed from subjects in the placebo group using the SAS PROC MI procedure with MNAR statement. This assumes that the missing data will follow a similar profile as the placebo group.

After the completion of the imputation, the assessments collected after the discontinuation of study treatment yet before to the use of rescue medication will be restored. The example code can be found in Appendix II.

The categorical secondary endpoints will be derived from the imputed scores in each MI datasets.

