### Sensitivity Analyses

Similar to primary efficacy endpoint, missing PP-NRS will be imputed using the multiple imputation (MI) with analysis of covariance (ANCOVA) model. MI will be performed under missing at random (MAR) assumption.

The Week 16 data of each of the 100 complete imputed datasets will be analyzed using an ANCOVA model with treatment, randomization strata, and baseline PP-NRS value included in the model, and the SAS MIANALYZE procedure will be used to generate valid statistical inferences by combining results from the 100 analyses using Rubin's formula.

The percent change from baseline in PP-NRS will also be analyzed using MMRM without imputation. The model will include factors (fixed effects) for treatment, randomization strata, visit, treatment-by-visit interaction, and baseline PP-NRS score. An unstructured covariance matrix will be used to model the within-patient errors. Denominator degrees of freedom will be estimated using approximation of SATTERTH. The efficacy data will be set to missing after rescue medication or procedure is used or after study withdrawal. Afterwards no imputation will be made.

The MMRM model will provide baseline adjusted least-squares (LS) means at Week 16 and at other time points for each treatment group with the corresponding standard error and the confidence interval, as well as the p values for treatment comparisons. The graph of LS-mean +/- SE by visit will be provided.

Other following sensitivity analyses will be planned for the key secondary using the ANCOVA or logistic model mentioned above, as applicable:

- In FAS, using PMM-MI and including site as a factor in the ANCOVA model.
- PP analysis set, using MI for handling missing data for all key secondary endpoints.
- In FAS, the LOCF and WOCF methods for handling missing data for continuous endpoints.

- In FAS, the TF method for handling missing data for binary endpoints.
- In FAS, the Observed-Cases (OC) approach for all endpoints. No imputation for missing data at any time point.

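### For vIGA 0/1 and EASI-75 the SAP declares a difference in response percentages but specifies only an odds ratio, so the declared summary has no planned confidence interval

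*SAP*

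**What the plan says.** SAP II.A introduces its estimand table as follows: "The main estimands associated with the primary and key secondary endpoints to support regulatory decisions are described in the following table". For the two binary key secondary endpoints the population-level summaries are "Difference in percentage of subject achieving vIGA of 0 or 1 between each RPT193 dose and placebo at Week 16" and "Difference in percentage of subject achieving EASI-75 between each RPT193 dose and placebo at Week 16".

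SAP VI.D.1 says the key secondary analysis "will use control-based PMM-MI for both categorical and continuous endpoints to handle missing data". Under SAP IV.D.2, "The categorical secondary endpoints will be derived from the imputed scores in each MI datasets". The binary model is a logistic regression on treatment, baseline vIGA stratum, prior dupilumab or tralokinumab use, and the baseline score where it is not already in the model. The log odds ratio and its standard error are pooled by Rubin's formula, and then "The combined results will be back transformed such that the odds ratio, 95% CI and p-value are reported". The sensitivity analyses keep the same model: "Other following sensitivity analyses will be planned for the key secondary using the ANCOVA or logistic model mentioned above, as applicable".

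For the primary endpoint, SAP VI.C says: "The LS mean and LS mean difference along with the 95% confidence interval (CI) and p-value will be reported". SAP VI.D.1 analyses PP-NRS in the same way.

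Protocol 9.4.2.1 prescribes logistic regression for binary secondary endpoints without naming an effect measure. Protocol 9.4.2 defines an estimand only for the primary endpoint.

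**The concern.** The estimand and the estimator are on different scales. The declared summary is an absolute, marginal quantity: how many more subjects per hundred respond on a dose than on placebo. The specified output is a relative quantity, conditional on covariates. The null hypothesis is the same for both, because an odds ratio of 1 means a zero difference, but the estimate and its interval are not.

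Under SAP IV.G the secondary endpoints carry no multiplicity adjustment, so their interpretation rests on estimates and intervals. The trial is dose-ranging and is meant to inform the design of later studies, for which absolute response differences matter. If the method stays open, the choice among a crude, a stratum-weighted and a standardised difference could be made after unblinding.

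**Working it through.** **1. Text comparison.**

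| Endpoint | Summary declared in SAP II.A | Output specified | Match |
|---|---|---|---|
| EASI % change (primary) | Difference in means | LS mean difference, 95% CI, p-value (VI.C) | Yes |
| PP-NRS % change | Difference in means | As for the primary (VI.D.1) | Yes |
| vIGA 0/1 | Difference in percentages | Odds ratio, 95% CI, p-value (VI.D.1) | No |
| EASI-75 | Difference in percentages | Odds ratio, 95% CI, p-value (VI.D.1) | No |

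The remaining places where a difference could be specified do not contain one:
- SAP I.C (changes from protocol) is silent.
- SAP IV.D.2 covers only the derivation of responder status.
- SAP IV.J gives counts and percentages, and says summary tables follow the later sections.
- SAP VI.B lists analysis sets and imputation methods.
- SAP VI.D.2 is descriptive.
- The Appendix II example for combining imputed results is a linear model.

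**2. What the odds ratio leaves open.** The documents give no response rates for these endpoints, so every rate below is an assumption. Only n = 67 per arm comes from the SAP (III.C). The calculation is unadjusted with complete data, so it illustrates scale and is not the result VI.D.1 would produce.

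The difference is p1 − p0, with SE = √[p0(1−p0)/67 + p1(1−p1)/67]. The odds ratio CI uses expected cell counts, with SE of the log odds ratio = √(sum of reciprocal counts).

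For 10% vs 25%, SE = √(0.10×0.90/67 + 0.25×0.75/67) = 0.0644, so the 95% CI is 0.150 ± 1.96×0.0644 = 0.024 to 0.276. The odds ratio is (0.25/0.75)/(0.10/0.90) = 3.00, with CI 1.14 to 7.92.

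| Placebo vs active | Difference, points (95% CI) | Odds ratio (95% CI) |
|---|---|---|
| 5% vs 15% | 10.0 (about 0 to 20.0) | 3.35 (0.93 to 12.15) |
| 10% vs 25% | 15.0 (2.4 to 27.6) | 3.00 (1.14 to 7.92) |
| 15% vs 35% | 20.0 (5.7 to 34.3) | 3.05 (1.32 to 7.05) |

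Conversely, with p1 = OR×odds0/(1 + OR×odds0), an odds ratio of 2.5 implies a difference of 6.6 points at 5% placebo response and 21.7 points at 30%.

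**3. Could a reader convert the adjusted odds ratio?** Take a conditional odds ratio of 3 and two vIGA strata. With placebo rates of 25% and 5% and weights 0.6 and 0.4, the overall placebo rate is 0.17. The active rates are 0.50 and 0.136, which average 0.3545, so the true difference is 0.1845. Applying the odds ratio of 3 to 0.17 gives 0.3806, a difference of 0.2106, which is 2.6 points too large. Three other assumed mixes give:
- 30%/5%, weight 0.6 on the first stratum: 0.192 true vs 0.229 converted.
- 30%/10%, weight 0.6: 0.218 vs 0.238.
- 20%/5%, weight 0.65: 0.179 vs 0.194.

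The error is 1.5 to 3.7 points, small against an interval about 25 points wide (27.6 − 2.4 = 25.2). The main loss is the missing interval, not bias.

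**4. Does the obvious remedy work?** It was simulated with 2000 trials per scenario, four arms of 67, and dropout after Week 12 more likely in worse subjects. Week 16 EASI change was imputed 100 times from the placebo regression and EASI-75 derived. A standardised difference with a delta-method SE was then taken from the logistic model and pooled by Rubin's formula. All inputs are assumed, and the truth is the control-based difference.

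| Placebo vs active, missing | True | Mean estimate | Pooled SE / empirical SD | Coverage |
|---|---|---|---|---|
| 13.0% vs 28.3%, 9.8% | 0.153 | 0.154 | 0.0689 / 0.0685 | 95.4% |
| Same setting, 18.4% | 0.149 | 0.147 | 0.0700 / 0.0643 | 96.3% |
| 5.4% vs 14.6%, 11.5% | 0.092 | 0.092 | 0.0513 / 0.0502 | 95.4% |

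The sparse setting with 21.7% missing had 97.0% coverage. In about 3% of sparse trials some imputed dataset had an arm with no responders. The share of trials with p < 0.05 for the difference vs the log odds ratio was 61.8% vs 58.3% in the first scenario and 41.6% vs 31.6% in the sparse one with 11.5% missing. The two Wald tests are therefore not interchangeable. Rescue use, intermittent missing data, the logistic imputation of vIGA and a wrong imputation model were not tested.

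**The case against.** The best reply is that little is lost. The SAP also runs treatment-failure and observed-case analyses for both endpoints, and lists EASI-75 at Week 16 again under other secondary endpoints. SAP IV.J displays counts and percentages, so a reader could build a crude difference and CI by hand. That is true, but such an interval answers a different question. Treatment-failure counts score every missing or post-rescue value as non-response, and observed-case analysis drops those values, whereas the declared estimand imputes them from the placebo profile. Under the primary imputation, the between-imputation variance cannot be recovered from summary tables.

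The table shells, which were not available, might show a difference. SAP IV.J cites them only for display standards and precision, and an estimator belongs in the plan itself.

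Three points stand:
- The test of no effect addresses the same null, and the logistic model follows the protocol.
- Renaming the summary in SAP II.A would also remove the inconsistency.
- Reporting a difference CI beside a logistic p-value can produce disagreement. In the sparse scenario this happens in at least 41.6 − 31.6 = 10.0% of simulated trials, so the SAP must say in advance how to read it.

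**Conclusion.** The concern holds: the SAP is internally inconsistent as written. Two of its three key secondary endpoints have no specified interval estimate of their declared summary under any imputation method, while the continuous endpoints do. This rests on the SAP text alone. The sizes shown depend on assumed rates: similar odds ratios near 3 accompany differences from 10 to 20 points, with intervals roughly 20 to 29 points wide at 67 per arm. The consequence is confined to estimating and reporting these two endpoints, which sit outside the gatekeeping. It should be corrected, but it does not threaten the primary conclusion.

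**What to change.** Add to the binary-endpoint paragraph of SAP VI.D.1:
- In each of the 100 control-based imputed datasets, average the predicted response probabilities by arm from the planned logistic model. Take the difference for each dose vs placebo with a delta-method standard error, and combine by Rubin's formula.
- Report that difference with its 95% CI, the arm percentages and the planned odds ratio.
- State that the p-value stays with the logistic model, and how a CI and p-value that disagree will be read.
- Give a rule for an imputed dataset in which an arm has no responders.

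A stratum-weighted difference pooled the same way would also serve; what matters is fixing one method in advance. The vIGA endpoint deserves a short check of its own, because its logistic imputation was not covered by the simulation. If the sponsor wants the odds ratio as the summary, SAP II.A should say so instead.

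SAP I.B allows changes until unblinding, and the Week 16 efficacy results go to an unblinded sponsor group before study end (IV.F), so the change should precede that analysis. The cost is SAP wording and a little programming, with no effect on data collection, sample size or subjects.
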